2. OBJECTIVES

2.1 Primary Objectives

- To assess the safety and tolerability of N-acetylcysteine (NAC) in patients with RP

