3.3 SAFETY PLAN

The safety assessments to be conducted for this study are listed in Section 5

Potential safety issues are associated with anterior chamber taps and peripheral blood draw. Subjects will be instructed to contact their physician at any time should they have health-related concerns. All adverse events (serious and non-serious) will be recorded for up to 14 days after the last study visit.

Anterior chamber tap in the clinic in patients with RP

The patient will be seated at a slit lamp and a drop of topical anesthetic will be placed in the study eye. A 30 gauge needle will be passed through the limbus into the anterior chamber and 0.15 ml of aqueous humor will be removed. There are no nerves at the limbus below the epithelium and therefore the topical anesthetic provides complete anesthesia and there is no pain associated with the procedure. Anterior chamber tap is a routine procedure that is extremely safe. It is done to deal with severe

increased intraocular pressure after intravitreal injections, or injection of gas during pneumatic retinopexy. Anterior chamber taps have been done as part of several prior studies and there have been no related complications or adverse events.

Peripheral blood draw

The peripheral blood will be drawn to collect RNA and DNA samples and serum bilirubin levels at the screening visit (BL-28 to 56 days). Blood draw for measurement of serum carbonyl content and GSH/GSSG ratio will be performed at each study visit. At the baseline (Day 1 +7days), week 12 and week 24 visit, peripheral blood will be drawn before as well as 1 and 2 hours after administration of oral NAC in the clinic for measurement of plasma NAC levels. The 2 hour blood draw will be optional, based on the convenience of the subject and at the discretion of the investigator. The peripheral blood draw is commonplace procedure and there are no risks to exposure to transmissible diseases if ones blood is being drawn using aseptic conditions. A patient may feel light headed or faint, or experience pain or discomfort at the site of puncture during the procedure. There may be possible bruising or swelling at the puncture site, rarely there may be an infection.

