3.4 COMPLIANCE WITH LAWS AND REGULATIONS

This study will be conducted in accordance with current U.S. Food and Drug Administration (FDA) Good Clinical Practices (GCPs), and local ethical and legal requirements.

4. **MATERIALS AND METHODS**

4.1 **SUBJECTS**

4.1.1 **Subject Selection**

Thirty eligible subjects with RP will be enrolled. Subjects will be identified and recruited through the clinic population at the Wilmer Eye Institute and it is expected that enrollment will be completed over an 12 month period.

4.1.2 **Inclusion Criteria**

All subjects must meet the following criteria to be eligible for study entry:

- Signed informed consent and authorization of use and disclosure of protected health information
- Age ≥ 18 years
- Patients diagnosed with RP by the investigators, based on clinical phenotype and diagnostic tests

4.1.3 **Exclusion Criteria**

Subjects who meet any of the following criteria will be ineligible for study entry:

- Patients with concurrent retinal pathologies that result in vision loss, including but not limited to retinal vein occlusion, diabetic retinopathy and neovascular age-related macular degeneration. If one eye does not have any retinal pathology other than RP, it may be enrolled in the study.
- Patients with uncontrolled arterial hypertension defined as diastolic blood pressure > 95 mm Hg or systolic blood pressure > 160 mm Hg despite medical therapy.

4.2 **STUDY ASSESSMENTS**

For a complete overview of the study assessments, see Flow Charts in Appendix section.

Screening Visit

- Obtain Informed Consent
- Record demographics, medical and ocular history; concomitant medications, smoking history, alcohol intake and supplement usage

- Vital sign measurements (blood pressure, pulse rate, temperature and respiratory rate)
- Slit lamp examination
- Indirect Ophthalmoscopy
- BCVA by Early Treatment Diabetic Retinopathy Study (ETDRS) Protocol
- SD-OCT
- Fundus autofluorescence
- Ultrawide field fundus photography
- MP1 and MAIA microperimetry
- Anterior chamber tap (for measurement of carbonyl content and GSH/GSSG)
- Blood draw for RNA and DNA samples, serum carbonyl content, GSH/GSSG ratio and bilirubin levels.

Baseline Visit (Day 1)

- Record any change in medical and ocular history; concomitant medications, smoking history, alcohol intake, supplement usage and adverse events
- Vital sign measurements (blood pressure, pulse rate, temperature and respiratory rate)
- Slit lamp examination
- Indirect Ophthalmoscopy

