- BCVA by Early Treatment Diabetic Retinopathy Study (ETDRS) Protocol
- SD-OCT
- MP1 and MAIA microperimetry
- Anterior chamber tap (for measurement of carbonyl content and GSH/GSSG)
- Obtain blood for serum carbonyl content, GSH/GSSG ratio and blood for plasma NAC Levels (before and after drug administration).
- Initiation of NAC treatment, first dose of NAC to be administered in the clinic

Four Week Visit (Week 4/ 28±7days)

- Record any change in medical and ocular history; concomitant medications, smoking history, alcohol intake, supplement usage and adverse events
- Vital sign measurements (blood pressure, pulse rate, temperature and respiratory rate)

- Slit lamp examination
- Indirect Ophthalmoscopy
- BCVA
- MAIA microperimetry
- Anterior chamber tap (for measurement of carbonyl content and GSH/GSSG)
- Blood Draw for serum carbonyl content and GSH/GSSG ratio

Eight Week Visit (Week 8/ 56±7days)

- Record any change in medical and ocular history; concomitant medications, smoking history, alcohol intake, supplement usage and adverse events
- Vital sign measurements (blood pressure, pulse rate, temperature and respiratory rate)
- Slit lamp examination
- Indirect Ophthalmoscopy
- BCVA
- MAIA microperimetry
- Anterior chamber tap (for measurement of carbonyl content and GSH/GSSG)
- Blood Draw for serum carbonyl content and GSH/GSSG ratio

Twelve Week Visit (Week 12/ 84±7days)

- Record any change in medical and ocular history; concomitant medications, smoking history, alcohol intake, supplement usage and adverse events
- Vital sign measurements (blood pressure, pulse rate, temperature and respiratory rate)
- Slit lamp examination
- Indirect Ophthalmoscopy
- BCVA
- SD-OCT
- MAIA microperimetry
- Anterior chamber tap (for measurement of carbonyl content and GSH/GSSG)
- Obtain blood for serum carbonyl content, GSH/GSSG ratio and blood for plasma NAC levels (before and after drug administration).

- NAC to be administered in the clinic

Sixteen Week Visit (Week 16/ 112±7days)

- Record any change in medical and ocular history; concomitant medications, smoking history, alcohol intake, supplement usage and adverse events
- Vital sign measurements (blood pressure, pulse rate, temperature and respiratory rate)
- Slit lamp examination
- Indirect Ophthalmoscopy
- BCVA
- MAIA microperimetry
- Anterior chamber tap (for measurement of carbonyl content and GSH/GSSG)
- Blood Draw for serum carbonyl content and GSH/GSSG ratio

Twenty Week Visit (Week 20/ 140±7days)

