4.5 STATISTICAL METHODS

4.5.1 Safety Analysis

The primary outcome measure is the safety and tolerability of N-acetyl cysteine (NAC) in patients with RP. Adverse events and results of ocular examinations from all 30 patients will be utilized to summarize safety data. The number and percentage of patients with treatment emergent adverse events (i.e. started or increased in severity after the patient received study treatment and includes abnormal lab results etc) will be summarised. The adverse events recorded prior to NAC administration will not be summarised and will be separated from the adverse events that are recorded post NAC administration in the final listings.

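### The adverse event summary leaves out the only pre-drug window and pools 12 off-drug weeks with treatment, so its percentage cannot separate NAC from background and tap events

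*Combined protocol and SAP*

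**What the plan says.** The primary objective (Section 2.1) is: "To assess the safety and tolerability of N-acetylcysteine (NAC) in patients with RP". Section 3.2.1 makes adverse event incidence and severity part of the primary outcome, together with changes from baseline in vital signs and physical examination.

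For adverse events, Section 4.5.1 plans one summary: "The number and percentage of patients with treatment emergent adverse events". An event counts if it began or worsened after the patient received study treatment. The definition gives no end date. Events before the first dose are handled by a separate rule: "The adverse events recorded prior to NAC administration will not be summarised and will be separated from the adverse events". The sentence ends by saying where they will appear: "separated from the adverse events that are recorded post NAC administration in the final listings".

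The schedule provides a drug-free run-in. Section 3.3 times the first blood samples "at the screening visit (BL-28 to 56 days". The Section 4.2 screening list already includes "Anterior chamber tap (for measurement of carbonyl content and GSH/GSSG". At the Baseline Visit the staff record changes in "concomitant medications, smoking history, alcohol intake, supplement usage and adverse events", and that list ends with "Initiation of NAC treatment, first dose of NAC to be administered in the clinic".

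Section 3 describes three dose cohorts, all on NAC, with a 12-week observation period after treatment. Appendix A shows paracentesis of the study eye at all 11 visits from screening to Week 36, and NAC treatment from Day 1 to Week 24.

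**The concern.** Summarising only treatment-emergent events is a normal convention. In a controlled trial it does little harm, because the control arm shows what patients report from the disease, the procedures and the passage of time. This trial has no such arm. What it has instead is time off drug in the same patients, on both sides of treatment. The plan gives the time before NAC no summary and merges the time after NAC with time on it.

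The primary question is about NAC. The planned percentage measures NAC together with ten taps (Day 1 to Week 36), repeated blood draws and about eight months of ordinary illness. Section 3.3 itself names taps and blood draws as sources of potential safety issues. A high percentage could arise with no drug effect, and a modest drug effect would not stand out.

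**Working it through.** The plan states no adverse event rate, so it has no figure of its own to reproduce. The rates below are assumptions, shown over a range.

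**Inputs from the documents.** 30 patients (4.5.1). Run-in of 28 to 56 days (3.3). NAC from Day 1 to Week 24, 168 days; observation to Week 36, a further 84 days, 252 in all (Appendix A). Taps: one at screening, seven from Day 1 to Week 24, three from Week 28 to Week 36. I assume that all 30 patients complete, and take 30.44 days per month.

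**Step 1. Patient-time and taps by period** (30 × days / 30.44)

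| Period | Person-months | Taps per patient | Taps in all | Planned handling |
|---|---|---|---|---|
| Run-in | 27.6 to 55.2 | 1 | 30 | listed, not summarised |
| On NAC | 165.6 | 7 | 210 | in the percentage |
| After NAC | 82.8 | 3 | 90 | in the same percentage |

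The Day 1 tap is placed with the on-NAC period because it falls at the visit where dosing starts. One third of the time behind the planned percentage (84/252) is scheduled to be off drug.

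**Step 2. Planned percentage with no NAC effect.** With a constant background rate r per person-month, the share of patients with at least one event by Week 36 is 1 − exp(−r × 252/30.44).

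- r = 0.1: 1 − exp(−0.828) = 56%
- r = 0.3: 1 − exp(−2.484) = 92%

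Over the 168 days on NAC alone the shares are 42% and 81%, so the off-drug weeks add 14 and 11 percentage points (56 − 42 and 92 − 81).

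**Step 3. Contribution of the taps.** With independent taps and per-tap risk p, the share of patients with at least one tap event over ten taps is 1 − (1 − p)^10: 10%, 18% and 40% for p = 1%, 2% and 5%.

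**Step 4. What a run-in rate could show.** Expected events are r × person-months, with exact Poisson 95% limits.

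| Assumed rate | Run-in | Events (rounded) | 95% interval per person-month |
|---|---|---|---|
| 0.1 | 28 days | 3 | 0.02 to 0.32 |
| 0.1 | 56 days | 6 | 0.04 to 0.24 |
| 0.3 | 28 days | 8 | 0.13 to 0.57 |
| 0.3 | 56 days | 17 | 0.18 to 0.49 |

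This gives a rough reference at the higher rate and a poor one at the lower.

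**Step 5. Whether the run-in can answer the tap question.** Thirty screening taps at p = 1%, 2% and 5% give 0.3, 0.6 and 1.5 expected events. The chance of seeing none, (1 − p)^30, is 74%, 55% and 21%. Zero events in 30 has an exact two-sided 95% upper limit of 1 − 0.025^(1/30) = 11.6%. The run-in cannot give a useful tap risk. The 90 post-NAC taps and the comparison of tapped with untapped eye offer more.

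**Step 6. Why rates and not percentages.** The run-in is one sixth to one third as long as the NAC period (28/168 to 56/168). At r = 0.1 with no drug effect, 9% to 17% of patients would have an event in the run-in and 42% on NAC. Raw percentages side by side would suggest a drug effect where there is none, so the table must use events per patient-time.

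**The case against.** A reader might infer that the plan discards the pre-drug events, or that the primary safety question has no pre-drug reference at all. The documents support neither. Section 4.5.1 keeps the events in the final listings, where in 30 patients they can be counted. Vital signs and physical examination are defined as changes from baseline, and the slit lamp, fundus and acuity examinations are done at both screening and Day 1. The gap concerns adverse event incidence only.

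The plan also has other aids to attribution. Section 5.1 asks the investigator to judge causality, and three cohorts with a step from twice to three times daily allow a look for a dose gradient. These help, but only in part. The causality question refers to the study intervention and allows a positive answer even where a procedure may be responsible. Section 4.5.1 plans no table by relatedness, dose, eye or period.

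The run-in is a weak comparator. Its events are captured once, at Day 1, by recall over up to 56 days, whereas later visits are roughly monthly and use a drug diary. The screening list has no adverse event item. If only treated patients are counted, anyone who left after a bad screening tap is missed. The event rates above have no source in the documents, and Section 3.3 reports no tap-related complications in prior studies. All of this stands. It limits the run-in rate to a descriptive use and rules it out as a tap-risk reference.

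Finally, the study is descriptive and tests no adverse event hypothesis, so no decision rule changes. That also stands, and it bears on how much weight the point deserves.

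**Conclusion.** The concern holds for adverse event incidence. The planned percentage has no summarised drug-free reference and mixes NAC with ten taps and 12 off-drug weeks. At assumed background rates of 0.1 to 0.3 per person-month, 56% to 92% of patients would have an event by Week 36 with no NAC effect. These figures assume a constant rate, independent events and 30 completers. The structural point does not depend on them: it follows from the rule, the open-ended definition and the absence of a control group.

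This is a worthwhile, inexpensive improvement to the primary safety report. It is not a defect that invalidates the trial. A reader might also expect the run-in alone to separate drug from tap events, but with 30 taps it cannot. The eye comparison and the post-NAC period have to carry that question.

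**What to change.** In Section 4.5.1, replace the sentence that excludes pre-NAC events from the summary with wording such as:

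- Adverse events will be summarised descriptively as events per person-month, with 95% intervals, overall and ocular, for three periods: screening to first NAC dose, on NAC, and after NAC to Week 36.
- Each patient's periods will follow the actual dates of first and last dose. The plan will state where events in the 14 days after the last visit, which Section 3.3 also records, are placed.
- Ocular events will be tabulated by study eye (tapped) and fellow eye (same oral NAC, no taps) where the eye is recorded.
- The separated listings stay as planned.

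The treatment-emergent percentage can remain beside this table.

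**Cost.** SAP wording and one or two tables, largely from data already collected, with no change to visits or procedures. The eye split depends on fellow-eye events being captured, which the documents do not spell out, so the case report form should be checked.

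**Limits to state with the table.** The run-in rate is imprecise and rests on one recall at Day 1, against roughly monthly visits later. Thirty screening taps cannot give a useful tap-risk reference. The post-NAC period may include carry-over.

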4.5.2 Secondary Analysis

To measure the change from baseline aqueous and serum carbonyl content and GSH/GSSG ratio at 1, 2, 3, 4, 5, 6, 7, 8 and 9 months after initiation of NAC treatment and correlate it with changes in BCVA, retinal sensitivity, and ellipsoid zone (EZ) width.

4.5.3 Power Analysis

Power analysis was conducted and a sample size of 30 was found to achieve 89% power to detect a mean of paired difference of 50% in aqueous carbonyl content with an estimated standard deviation of 0.8 and with significance level of 0.05 (95% confidence interval) using a 2 sided paired t-test.

4.5.4 Missing Data

Analyses of efficacy and safety will be based on available cases without imputation for missing values.

4.5.5 Interim Analysis

No formal schedule of interim analyses is planned. Reports of adverse events from this study may be reviewed and summarized periodically while the study is ongoing to ensure the safety of subjects.

4.5.6 Early Termination and Replacement of Subjects

Subjects withdrawn from the study prior to completion will be asked to return for an end of treatment assessment visit (all study procedures on the EOT assessment visit will be similar to those conducted on the month 9 visit) and the 3 months observational period. Subjects who are terminated prior to the week 24 visit will be replaced.

4.6 DATA QUALITY ASSURANCE

- Accurate, consistent, and reliable data will be ensured through the use of standard practices and procedures.

5. ASSESSMENT OF SAFETY

5.1 ADVERSE EVENTS

For this protocol, an AE is any “on study” untoward medical occurrence (e.g., sign, symptom, disease, syndrome, intercurrent illness) that occurs in a study subject, regardless of the suspected cause.

Unchanged, chronic conditions are NOT AEs and should not be recorded on the AE pages of the CRF. An exacerbation or worsening of a chronic condition should be recorded as an AE.

Both serious and non-serious AEs should be graded on a three-point scale (mild, moderate, severe) and reported in detail on the appropriate AE page of the CRF.

The suggested definitions are as follows:

Mild:	Discomfort noticed but no disruption of normal daily activity
Moderate:	Discomfort sufficient to reduce or affect normal daily activity
Severe:	Incapacitating with inability to work or perform normal daily activity

Using the following criteria, investigators also need to assess whether there is a reasonable possibility that study intervention caused or contributed to the AE.

- Yes (possibly or probably)

There is a clinically plausible time sequence between onset of the AE and study intervention; and/or

There is a biologically plausible mechanism for study intervention causing or contributing to the AE;
and

The AE may or may not be attributed to concurrent/underlying illness, other drugs, or procedures.

- No

A clinically plausible temporal sequence is inconsistent with the onset of the AE and study intervention;
and/or

A causal relationship is considered biologically implausible.

5.2 BASELINE MEDICAL CONDITIONS

It is not necessary to complete an AE CRF page for chronic medical conditions present at enrollment that do not worsen in intensity or frequency during the trial. These medical conditions should be adequately documented on the appropriate page of the CRF (medical history and/or physical examination). However, medical conditions present at enrollment that worsen in intensity or frequency during the treatment or post-treatment periods and ongoing AEs that started during the previous study should be reported and recorded as AEs.

5.3 PROCEDURES FOR RECORDING AND REPORTING ADVERSE EVENTS

5.3.1 Recording Adverse Events

To improve the quality and precision of acquired AE data, investigators should observe the following guidelines:

- Whenever possible, use recognized medical terms when recording AEs on the AE pages of the CRF. Do not use colloquialisms and/or abbreviations.
- If known, record the diagnosis (i.e., disease or syndrome) rather than component signs and symptoms on AE pages of the CRF (e.g., record congestive heart failure rather than dyspnea, rales, and cyanosis). However, signs and symptoms that are considered unrelated to an encountered syndrome or

disease should be recorded as individual AEs on the CRF (e.g., if congestive heart failure and severe headache are observed at the same time, each events should be recorded as an individual AE).

- AEs occurring secondary to other events (e.g., sequelae) should be identified by the primary cause. A “primary” AE, if clearly identifiable, generally represents the most accurate clinical term to record on AE pages of the CRF. If a primary serious AE (SAE) is recorded on an SAE CRF, events occurring secondary to the primary event should be described in the narrative description of the case.

5.3.2 Serious Adverse Events

An AE should be classified as **SERIOUS** if:

- It resulted in death (i.e., the AE caused or led to death).
- It was life threatening (i.e., the AE placed the subject at immediate risk of death; it does not apply to an AE that hypothetically might have caused death if it were more severe).
- It required or prolonged inpatient hospitalization (i.e., the AE required at least a 24-hour inpatient hospitalization or prolonged a hospitalization beyond the expected length of stay; hospitalizations for elective medical/surgical procedures, scheduled treatments, or routine check-ups are not SAEs by this criterion).
- It was disabling (i.e., the AE resulted in a substantial disruption of the subject’s ability to carry out normal life functions).
- It resulted in a congenital anomaly/birth defect (i.e., an adverse outcome in a child or fetus of a subject exposed to the molecule or study drug prior to conception or during pregnancy).
- It does not meet any of the above serious criteria but may jeopardize the subject or may require medical or surgical intervention to prevent one of the outcomes listed above.

Sight-threatening adverse events

An adverse event is considered to be sight-threatening if it meets one or more of the following criteria and will be reported as a serious adverse event (SAE):

- The event causes a decrease in visual acuity of greater >30 letters (compared with the last assessment of visual acuity prior to the most recent treatment) lasting >1 hour.

- The event causes a decrease in visual acuity to the level of light perception or worse lasting >1 hour.
- The event requires surgical intervention (e.g, conventional surgery, vitreous tap or biopsy with intravitreal injection of antibiotics, or laser or retinal cryopexy with gas) to prevent permanent loss of sight.
- The event is associated with severe intraocular inflammation (i.e., 4+ anterior chamber cell/flare or 4+ vitritis).
- In the opinion of the investigator, the event may require medical intervention to prevent permanent loss of sight.

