Cohort 3	1800mg bid	1800mg bid	1800mg bid	1800mg tid	1800mg tid	1800mg tid

There will be 8 study visits (screening, baseline and month 1-6), all study visits after the baseline visit will be 28±7 days apart, followed by a 12 week observation period. At each visit, patients will have medical history, measurement of vital signs (blood pressure, heart rate, respiratory rate and temperature), review of concomitant medications, review of study drug diary, recording of adverse events, BCVA, eye examination, and anterior chamber tap. MP1 microperimetry will be done at screening and baseline visit. Optical Coherence tomography will be done at the screening and baseline visit and repeated every 3 months. MAIA microperimetry will be done at screening and baseline visit and repeated every month. Fundus autofluorescence and Ultrawide field fundus photographs will be obtained at screening and month 6 visit. At all visits where needed, microperimetry will be performed first followed by OCT, FAF and UWFP. Serum levels of NAC pre- and post-dose will be measured at baseline, week 12 and 24. When all 10 subjects in cohort 1 have had a week 4 visit, the PI will review safety and tolerability with study team members and if there has been good safety and tolerability, enrollment will begin for cohort 2. When all 10 subjects in cohort 2 have had a week 4 visit, the PI will

review safety and tolerability with study team members and if there has been good safety and tolerability, enrollment will begin for cohort 3.

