- Record any change in medical and ocular history; concomitant medications, smoking history, alcohol intake, supplement usage and adverse events
- Vital sign measurements (blood pressure, pulse rate, temperature and respiratory rate)
- Slit lamp examination
- Indirect Ophthalmoscopy
- BCVA
- MAIA microperimetry
- Anterior chamber tap (for measurement of carbonyl content and GSH/GSSG)
- Blood Draw for serum carbonyl content and GSH/GSSG ratio

Twenty-Four Week Visit (Week 24/ 168±7days)

- Record any change in medical and ocular history; concomitant medications, smoking history, alcohol intake, supplement usage and adverse events
- Vital sign measurements (blood pressure, pulse rate, temperature and respiratory rate)
- Slit lamp examination
- Indirect Ophthalmoscopy

- BCVA
- SD-OCT
- Fundus auto-fluorescence
- Ultra-wide field fundus photography
- MAIA microperimetry
- Anterior chamber tap (for measurement of carbonyl content and GSH/GSSG)
- Blood Draw for serum carbonyl content, GSH/GSSG ratio and blood for plasma NAC levels (before and after drug administration)
- NAC to be administered in the clinic

Twenty-Eight Week Visit (Week 28/ 196±7days)

- Record any change in medical and ocular history; concomitant medications, smoking history, alcohol intake, supplement usage and adverse events
- Vital sign measurements (blood pressure, pulse rate, temperature and respiratory rate)
- Slit lamp examination
- Indirect Ophthalmoscopy
- BCVA
- MAIA microperimetry
- Anterior chamber tap (for measurement of carbonyl content and GSH/GSSG)
- Blood Draw for serum carbonyl content and GSH/GSSG ratio

Thirty-Two Week Visit (Week 32/ 224±7days)

- Record any change in medical and ocular history; concomitant medications, smoking history, alcohol intake, supplement usage and adverse events
- Vital sign measurements (blood pressure, pulse rate, temperature and respiratory rate)
- Slit lamp examination
- Indirect Ophthalmoscopy
- BCVA
- MAIA microperimetry
- Anterior chamber tap (for measurement of carbonyl content and GSH/GSSG)

- Blood Draw for serum carbonyl content and GSH/GSSG ratio

Thirty-Six Week Visit (Week 36/ 252+7days)

- Record any change in medical and ocular history; concomitant medications, smoking history, alcohol intake, supplement usage and adverse events
- Vital sign measurements (blood pressure, pulse rate, temperature and respiratory rate)
- Slit lamp examination
- Indirect Ophthalmoscopy
- BCVA
- SD-OCT
- MAIA microperimetry

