5.3.4 Type and Duration Of Follow-Up After Adverse Events

All reported AEs should be followed until resolution or until 1 month after the procedure. Subjects who have an ongoing study related SAE will be followed by the investigator or his or her designee until the event is resolved or determined to be irreversible, chronic, or stable by the investigator.

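### Birth defects are a listed SAE, but most term births after conception on NAC would fall after adverse event recording closes, and no pregnancy reporting or outcome follow-up is planned

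*Combined protocol and SAP*

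**What the plan says.** All references are to the combined protocol and SAP.

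- **Criterion.** Section 5.3.2 lists congenital anomaly or birth defect as an SAE criterion: "an adverse outcome in a child or fetus of a subject exposed to the molecule or study drug prior to conception or during pregnancy". It covers a fetus as well as a child, and exposure before conception as well as during pregnancy.
- **End of recording.** Section 3.3: "All adverse events (serious and non-serious) will be recorded for up to 14 days after the last study visit".
- **Follow-up of recorded events.** Section 5.3.4: "All reported AEs should be followed until resolution or until 1 month after the procedure". Longer follow-up is given only to a study-related SAE that is already ongoing.
- **Exposure.** Section 4.2 starts treatment at the Day 1 visit: "Initiation of NAC treatment, first dose of NAC to be administered in the clinic". The last visit with treatment marked, there and in Appendix A, is "Twenty-Four Week Visit (Week 24/ 168±7days").
- **Last visit.** Section 4.2 ends with "Thirty-Six Week Visit (Week 36/ 252+7days"). Appendix A gives that visit ±7 days and marks adverse events through it. Section 3 counts differently: "There will be 8 study visits (screening, baseline and month 1-6"), "followed by a 12 week observation period".
- **Pregnancy.** Entry is open to adults (section 4.1.2). Neither eligibility list nor any row of Appendix A mentions pregnancy, and sections 3.3 and 5 contain no procedure for reporting a pregnancy or following it to its outcome.

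**The concern.** The criterion and the recording window do not fit together. A birth defect usually becomes an event at or near birth, and a pregnancy that begins during a 24-week treatment period will mostly end after a window that closes about 38 weeks after the first dose (266 / 7). Section 5.3.4 does not bridge the gap. Section 5.1 defines an AE as an untoward occurrence in a subject, so an uneventful pregnancy on the closing day is not an ongoing SAE and nothing keeps the record open.

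Safety and tolerability is the primary outcome. A final report of no birth-defect SAEs could mean that none occurred, or only that recording stopped first, and the reader could not tell which. The gap applies to pregnancies of female subjects and, because the criterion covers exposure before conception, to children of male subjects.

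**Working it through.** **The plan's own dates.** 36 × 7 = 252 and 24 × 7 = 168, so the stated visit days agree with the week labels. The gap of 12 weeks matches the stated observation period.

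**Close of recording.** 252 + 14 = Day 266. With ±7 days (Appendix A) the range is 259 to 273; with +7 only (section 4.2) it is 266 to 273.

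**Assumption.** Pregnancy length is not in the documents. I take conception at 2 weeks' gestation, so birth at 37, 38, 39 or 40 weeks comes 245, 252, 259 or 266 days after conception.

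**Formula.** Latest conception day with birth inside the window = closing day − days from conception to birth. Share = that day / 168, treating conception as equally likely on each treatment day.

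| Birth at | Days after conception | Close Day 259 | Close Day 266 | Close Day 273 |
|---|---|---|---|---|
| 37 weeks | 245 | Day 14 (8.3%) | Day 21 (12.5%) | Day 28 (16.7%) |
| 38 weeks | 252 | Day 7 (4.2%) | Day 14 (8.3%) | Day 21 (12.5%) |
| 39 weeks | 259 | none (0%) | Day 7 (4.2%) | Day 14 (8.3%) |
| 40 weeks | 266 | none (0%) | none (0%) | Day 7 (4.2%) |

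The captured share is 0 to 16.7%, so about 83 to 100% of term births from on-treatment conceptions come after the close. A conception on Day 168 with a 266-day interval ends on Day 434, which is 434 − 266 = 168 days after the nominal close. Conceptions after Day 168, which the criterion also covers, cannot reach term in time: 168 + 245 = 413, against a latest close of 273.

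**If the last study visit is month 6.** 168 + 14 = Day 182. Even the shortest interval gives 182 − 245 = −63, so no term birth from an on-treatment conception is captured.

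**If visit spacing drifts.** Section 3 spaces visits 28 ± 7 days apart. Stretching every interval to 35 days, outside the fixed windows of section 4.2 and Appendix A, puts the ninth post-baseline visit on Day 315, the close on Day 329 and the last treatment visit on Day 6 × 35 = 210. The captured share is then (329 − 266) / 210 = 30% to (329 − 245) / 210 = 40%, still a minority.

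**What the window can capture.**
- *Fetal findings.* A scan at 18, 20 or 22 weeks (assumed timing; none is scheduled) comes 112, 126 or 140 days after conception. It precedes Day 266 for conceptions up to Day 154, 140 or 126, which is 91.7%, 83.3% or 75.0% of treatment days.
- *Pregnancies present at entry.* Birth at 40 weeks (280 days' gestation) falls by Day 266 if gestation on Day 1 is at least 280 − 265 = 15 days.

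**The case against.** The strongest reply has three parts.

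*The criterion still works.* A reader might infer that no full-term pregnancy conceived on NAC can end before recording closes, or that the birth-defect criterion can never be met. The documents support neither. Births at 37 to 39 weeks after conception in the first one to three weeks fall inside the nominal window. A 40-week pregnancy conceived on Day 1 ends on Day 267, one day after the nominal close and inside the +7 close. The criterion also names the fetus and exposure during pregnancy, so prenatal findings, losses and pregnancies present at entry can be recorded. This part stands and limits the point to term births after on-treatment conception.

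*Other reporting duties carry no end date.* Section 5.3.3 requires SAE reporting within 48 hours of learning of the event, and sections 5.3.4 to 6.4 do not clearly release an investigator who hears of a birth defect later: 5.3.5 and 6.4 require IRB notification without a time limit. This stands in part. Those duties act only on what investigators happen to learn, no contact is scheduled after the last visit, and nothing reconciles them with the limit in section 3.3.

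*Little is at stake numerically.* Every percentage above is conditional on a conception, the documents give no expected number, and section 5.3.2 classifies seriousness rather than setting an endpoint. This stands as an argument for modest priority, not for leaving the mismatch. Nor can it be inferred that subjects receive no instruction about pregnancy: the consent form is not in the text reviewed.

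**Conclusion.** The concern holds in limited form. The protocol classes a birth defect after exposure as serious, yet its recording limit would miss about 83 to 100% of term births from conceptions during treatment, and it plans no pregnancy reporting or outcome follow-up that would recover them. If the last study visit is month 6, it misses all of them. Week 36 is the more natural reading, since Appendix A marks adverse events to that visit and section 4.5.6 refers to a month 9 visit, but the text should say so.

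The range rests on three assumptions: term birth 245 to 266 days after conception, conception spread evenly over the 168 treatment days, and the fixed visit windows of section 4.2 and Appendix A. It says nothing about how likely a pregnancy or a birth defect is, and nothing in the documents shows that NAC harms a pregnancy. With 30 subjects and few pregnancies expected, this is a worthwhile but modest correction.

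**What to change.** - **Sections 5.3.2 and 5.3.3.** Require that any pregnancy of a subject that is present on Day 1, or conceived up to the end of AE recording, is reported to the PI and followed to its outcome. Apply the same to a partner's pregnancy, with the partner's permission. The pregnancy itself need not be classed as an SAE; an outcome that meets the criterion would be.
- **Sections 3.3 and 5.3.4.** Exempt these outcomes from the 14-day and 1-month limits.
- **Section 4.5.1.** List pregnancy outcomes in the safety summary, including those that arrive after the last visit.
- **Sections 3 and 3.3.** State which visit is the last study visit, and reconcile the count of 8 visits to month 6 with the visits to Week 36.

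This changes recording only. It proposes no change to eligibility, testing or treatment.

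The cost is protocol wording, one report form, occasional telephone contact, and a consent and IRB wording change so that partner information can be collected. The downside is that a few records stay open after the last visit, up to about 168 days past the nominal close for a conception on the last treatment day, and longer for a conception later in the recording period.
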